9.5. Study size

The target sample sizes for the HCP and patient populations are 280 completed surveys for each population. This sample size was determined based on the width of confidence intervals it will provide. [Table 1](#) shows 2-sided 95% confidence intervals based on the normal approximation to the binomial distribution ([Equation 1](#)) for a single sample of size of 280.

The samples will be divided by countries according to the distribution of eligible participants in each country. The EDC system will be programmed with country-specific limits to ensure desired distribution. Both unweighted and weighted results will be presented in the final report.

Equation 1.

$$95\%CI = Response\ Rate \pm 1.96 \left\{ \sqrt{\left[\frac{Response\ Rate(1-Response\ Rate)}{Sample\ Size} \right]} \right\}$$

Table 1. Sample size calculations

Sample Size	Observed Response Rate* (e.g. Knowledge)	2-Sided 95% Confidence Interval		
		Half-width	Lower Limit	Upper Limit
280	50%	5.9%	44.1%	55.9%
	60%	5.7%	54.3%	65.7%
	70%	5.4%	64.6%	75.4%
	80%	4.7%	75.3%	84.7%
	90%	3.5%	86.5%	93.5%

*Percentage of responders who correctly answered a question.

9.6. Data management

All data collected during the survey will be held confidentially by UBC. The EDC system used for data collection encrypts all respondent-identifying information, and respondent identifiers are stored separately from the survey responses. No identifiable information will be required from patients, but will be collected if they are eligible to and wish to receive payment, if offered based on local laws and regulations. The data from the surveys collected will be stratified by country as well as combined for analysis in a final study report for each stakeholder population.

The survey is programmed to ensure Internet and telephone respondents cannot skip ahead and will only allow for missing data when caused by skip patterns. Paper surveys, if used, will have instructions to guide respondents through the survey correctly in an effort to avoid missing data. In instances where there is missing data not due to skip patterns (that is, respondent did not complete the survey), the respondent will not be considered in the analysis.

Skip logic as well as the ability to mark only one response or multiple responses are part of the programming for the survey administration and minimise the occurrence of data entry errors. There will be no queries to respondents for this project.

9.7. Data analysis

Data collected from the survey will be reported as descriptive statistics. Frequency distributions with 95% CIs will be calculated for respondent responses to all questions that address the survey objectives. Responses to each question relating to the key risk messages will be categorised as “Correct response” and “Incorrect response”. “I don’t know” is generally categorised as an incorrect response unless otherwise specified.

In addition to the overall analysis, survey data will be analysed to determine if there are any differences by country and, for HCPs, medical speciality. Sub-group analyses will include all requested subgroups including patients switched from other 100 units/ml insulins, Humalog 100 U/ml, how long patients were on insulin, and which other insulins have been used as captured in the questionnaire. Additionally, a subgroup analysis will be performed to identify possible differences in the responses based on length of Humalog 200 units/ml use.

The following will be reported as part of the analysis:

HCPs:

- *Survey administration*
 - The number of survey invitations issued by strata (i.e., by country and specialty)
 - The number of survey invitations returned due to incorrect mailing address of HCPs invited to participate in the survey
 - The number of HCPs who responded to the invitation to participate in the survey
 - The number of HCPs eligible for participation in the survey
 - The number of ineligible HCPs along with the reasons for ineligibility
 - The number of eligible HCPs who completed the survey
- *Demographic characteristics of participants*
 - Distribution of participants by age groups
 - Distribution of participants by sex
 - Distribution of participants by practice setting
 - Distribution of participants by country
 - Distribution of participants by medical specialty
 - Distribution of participants by years in medical practice
 - Distribution of participants by number of patients treated with Humalog 200 units/ml KwikPen
- *Responses to questions pertaining to the survey objectives:*
 - Awareness of the DHPC on the correct use of Humalog (insulin lispro) 200 units/ml KwikPen
 - Understanding of the risk messages
 - Self-reported practices with respect to communication of the key risk messages in clinical practice

Patients:

- *Survey administration*
 - The number of HCPs asked to invite patients to participate
 - The number of invitations provided to HCPs
 - The number of patients who responded to the invitation to participate in the survey
 - The number of patients eligible for participation in the survey
 - The number of ineligible patients along with the reasons for ineligibility
 - The number of eligible patients who completed the survey

- *Demographic characteristics of participants*
 - Distribution of participants by age groups
 - Distribution of participants by sex
 - Distribution of participants by country
 - Distribution of participants by years with diabetes
 - Distribution of participants by length of time treated with any injectable insulin therapy
 - Distribution of participants by length of time treated with Humalog 200 units/ml KwikPen
 - Distribution of participants by insulin used prior to Humalog 200 units/ml KwikPen
- *Patient responses to questions pertaining to the survey objectives:*
 - Awareness of the Important Safety Information for Humalog 200 units/ml KwikPen
 - Receipt of or access to Important Safety Information including the source of this information
 - Understanding of the risk messages
 - Self-reported practices with respect to the risk messages

9.8. Quality control

Data will be collected using a secure online EDC system that has been developed and fully validated. A rigorous System Development Life Cycle (SDLC) is used for validation that complies with 23 internal IT Standard Operating Procedures (SOPs) of UBC. Unit testing and formal validation occur on all appropriate systems and components during the build stage. The SDLC is fortified with SOPs addressing validation for all clinical and risk minimisation-related applications. The Internet-based repository will be used to store survey data and other relevant programme information. The system is EudraLex Annex 11 (and 21 CFR Part 11 in the US) compliant for the entry, storage, manipulation, analysis and transmission of electronic information. This platform ensures compliance with all relevant regulatory guidelines. Respondent-identifying information is stored separately from survey data.

Programming will be reviewed by Quality Control and simulated users [User Acceptance Testing (UAT)] prior to implementation.

At the completion of data collection, data will be extracted from the EDC and mapped to SAS datasets (SAS V9.1.3 or higher). The mapping of raw data will be validated, as will the programming of the analysis tables created from the raw EDC data. The raw EDC data is used to populate analysis tables that are programmed by SSRS according to the statistical analysis plan (SAP). Additionally, the EDC data will also be mapped to SAS datasets by a SSRS programmer as defined in the aDCTs and validated by the QC team.

The UBC has an IT Quality Assurance Group that is responsible for managing and overseeing system/application development and validation, as well as related compliance functions.

9.9. Limitations of the research methods

The survey recruitment strategies are intended to recruit heterogeneous samples of HCPs prescribing or managing diabetic patients, and patients being treated with Humalog 200 units/ml KwikPen. The participants will be self-selected since they will voluntarily respond to the invitation to participate; however, those who read the invitation to participate are more likely to be attentive to all Humalog 200 units/ml KwikPen information, and therefore more compliant. Additionally, there is the potential to introduce bias in the patient results if only highly compliant HCPs recruit their patients for survey participation.

Additionally, inherent in survey research is the reliance on the respondent's recall for whether or not the risk minimisation communication was received in order to evaluate the scope of risk minimisation measures. If the respondent says she/he did not receive the communication, the risk minimisation programme is evaluated as not optimally disseminating material. It is possible, however, that respondents may simply not recall receiving the tools that were, in fact, received. It is also possible that they have acceptable understanding of the risks and appropriate behaviours despite not receiving or recalling receipt of the risk minimisation measure-specific communication. All data from the survey are self-reported and therefore susceptible to possible reporting bias. This is also applicable to the patients' self-reporting of their practice behaviours to minimise the risks. There may be discrepancies between what respondents report about their practices and their actual behaviours.

9.9.1. Controls to minimise bias

A number of controls will be in place to ensure the survey is conducted in a professional manner and to minimise bias, including the following:

- Lists of response options will be randomised to minimise the potential for positional bias.
- The Internet and telephone surveys will be programmed to ensure that questions are asked in the appropriate sequence and all questions will be presented in a standard order to reduce exposure bias. Respondents cannot skip ahead or go back to a question once the question has been answered. All questions presented must be answered in order to complete a survey. Not all questions may be presented due to skip logic within the survey.
- Respondents will be provided with a unique code during the recruitment process and will then be asked to provide the unique code in order to gain access to the Internet-based and telephone administration systems. The code will be inactivated after use to minimise exposure bias and fraud.
- Each HCP will only be provided 10 patient packets to minimise potential over-representation bias by highly compliant HCPs (Section 9.2).

9.10. Other aspects

Not applicable.

10. Protection of human subjects

10.1. Personal Information and Consent

All data collected during the survey will be held confidential by the survey administrator and used only for the purposes stated in the survey instructions. Respondent names and addresses are collected for the purposes of mailing a thank you letter and payment, if applicable, after the survey is completed. The EDC system used for data collection encrypts all identifiable information, and respondent identifiers are stored separately from the survey responses.

By answering the first question of the survey (“Do you agree to participate in this survey?”) after reading the introductory message (“Preamble 1”), respondents are acknowledging informed consent for participation in the research study.

If, during survey completion, UBC personnel are made aware of a safety event (SE), the UBC project personnel will follow the reporting structure described in Section 11. The respondent will be asked for consent to allow their contact information to be provided to Lilly, so that Lilly may contact them for additional information. If the consent is not granted, UBC personnel will report the SE with the information provided by the respondent.

10.2. Respondent withdrawal

Respondents can decline to participate or stop taking the survey at any time. Only complete surveys will be included in the analysis.

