| 
B My doctor or nurse offered to explain the information in IMPORTANT SAFETY INFORMATION FOR Humalog 200 units/ml KwikPen (insulin lispro).
 |  |  |  |
| 
C I think about the important safety information for Humalog 200 units/ml KwikPen to remind myself of the risks when injecting my insulin.
 |  |  |  |

16. Other than the information you received from your doctor or nurse, from what sources have you received and/or accessed information on the safe use and understanding of the *Humalog 200 units/ml KwikPen*. Please select all that apply

Pharmacist

Other Medical Professional

Diabetes Support Group

Internet

Other

[PHONE ONLY: BEGIN SAFETY EVENT/PRODUCT COMPLAINT]

(INTERVIEWER: Please record if respondent spontaneously reported a safety event or product complaint during the course of this interview.)

- Yes
- No **[GO TO CLOSING 1a]**

Enter Safety Event or Product Complaint Verbatim

[MULTILINE INPUT]

(INTERVIEWER: Refer to Project Specific Procedure for next steps.)

[END SAFETY EVENT/PRODUCT COMPLAINT]

[CLOSING 1 DISPLAY ONLY IN [ENTER COUNTRIES OFFERING PAYMENT]]

We would like to send you [AMOUNT/TYPE] as compensation for your time and effort, but need your name and address to do so. Do you agree to provide your contact information for this purpose?

- Yes
- No **[GO TO CLOSING]**

FIRST NAME: **[FREE TEXT]**

LAST NAME: **[FREE TEXT]**

MIDDLE INITIAL: **[OPTIONAL; MUST BE 1-DIGIT ALPHA CHARACTER]**

ADDRESS: **[MULTILINE INPUT]**

CITY: **[FREE TEXT]**

COUNTRY: **[DROP-DOWN LIST INPUT WITH COUNTRIES TABLE]**

POSTAL CODE: **[FREE TEXT]**

[CLOSING 2]

This completes the survey. Thank you again for your participation.

[END SURVEY CONTENT]

**APPENDIX I.5 DIRECT HEALTHCARE PROFESSIONAL COMMUNICATION
ON THE CORRECT USE OF *HUMALOG 200 UNITS/ML KWIKPEN***

**APPENDIX I.6 PATIENT COMMUNICATION: IMPORTANT SAFETY
INFORMATION FOR HUMALOG[®] 200 UNITS/ML KWIKPEN[™] (INSULIN LISPRO)**

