For point 11.1, the design of the EDC system is such that respondents must complete each answer before advancing so there will not be missing data.

Section 12: Limitations	Yes	No	N/A	Page Number(s)
12.1 Does the protocol discuss:				
12.1.1 Selection biases?				23-24
12.1.2 Information biases?				23-24
(e.g. anticipated direction and magnitude of such biases, validation sub-study, use of validation and external data, analytical methods)				
12.2 Does the protocol discuss study feasibility? (e.g. sample size, anticipated exposure, duration of follow-up in a cohort study, patient recruitment)				20-21
12.3 Does the protocol address other limitations?				23-24

Comments:

Section 13: Ethical issues	Yes	No	N/A	Page Number(s)
13.1 Have requirements of Ethics Committee/Institutional Review Board approval been described?				25

**Non-Interventional Study Protocol
for Humalog 200 units/ml KwikPen
Version 1.0**

Section 13: Ethical issues	Yes	No	N/A	Page Number(s)
13.2 Has any outcome of an ethical review procedure been addressed?				
13.3 Have data protection requirements been described?				23

Comments:

Section 14: Amendments and deviations	Yes	No	N/A	Page Number(s)
14.1 Does the protocol include a section to document future amendments and deviations?				12

Comments:

Section 15: Plans for communication of study results	Yes	No	N/A	Page Number(s)
15.1 Are plans described for communicating study results (e.g. to regulatory authorities)?				26
15.2 Are plans described for disseminating study results externally, including publication?				26

Comments:

Name of the main author of the protocol: [name]

Date:

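### Patient survey Q16 forces an answer but has no 'None' or 'I don't know', so patients with no source beyond their doctor or nurse must tick something untrue or stop

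*Protocol*

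**What the plan says.** **The question.** Protocol, Appendix I.3, Q16 begins: "Other than the information you received from your doctor or nurse, from what sources have you received and/or accessed information". The instruction is "Please select all that apply". The options are a pharmacist, another medical professional, a "Diabetes Support Group", the Internet, and other. No 'None', 'I don't know' or 'Prefer not to answer' is listed. No skip or display condition is attached, and 'Other' has no free-text marker.

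**Answering is compulsory.** Section 9.9.1: "All questions presented must be answered in order to complete a survey". The welcome page in Appendix I.3 tells patients the same and says they cannot return once they exit. Section 9.6 allows missing data in the Internet and telephone versions only where a skip pattern causes it. The Annex 2 comment on item 11.1 describes the data capture system in the same way: "respondents must complete each answer before advancing so there will not be missing data".

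**Incomplete surveys are dropped whole.** Section 9.6 says that where data are missing for any reason other than a skip, "the respondent will not be considered in the analysis". Section 10.2: "Only complete surveys will be included in the analysis".

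**Use of the item.** Section 9.7 lists the source of the safety information among the patient results to be reported.

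**The concern.** Q16 presupposes at least one source besides the doctor or nurse. Yet the risk minimisation programme is designed to reach patients through the prescriber, so patients with no other source are to be expected. Patients who received information from nobody are in the same position. None of them has a truthful answer to give.

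Two things are at stake. The first is the Q16 result itself, which would credit other sources that some patients never used. That matters for interpretation: Section 9.9 concedes that patients may understand the risks without having received the communication, and Q16 is the patient item that records other routes. The second is the position of Q16. It follows Q14 (understanding, the primary objective) and Q15 (receipt, explanation, behaviour). Under Sections 9.6 and 10.2, a patient who stops at Q16 forfeits answers to items that had no such fault.

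**Working it through.** **Step 1. Is there a truthful answer?** Take a patient with no source other than the doctor or nurse.

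| Route | What the Protocol provides | Result |
|---|---|---|
| Tick an option | Five options, none true for this patient | False record of a source |
| Tick 'Other' | No text field shown | Cannot be told from a real other source |
| Leave blank, Internet or telephone | Sections 9.6 and 9.9.1 and the welcome page do not allow it | Cannot proceed |
| Stop | No re-entry; Section 10.2 | Whole record dropped, Q14–Q15 included |
| Leave blank on paper | Missing and not caused by a skip; Section 9.6 | Whole record dropped |

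If the software did accept zero ticks, the record would survive, but 'no other source' would look the same as an item passed over.

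The omission is out of line with the rest of the instrument. Q14 and Q15 both offer 'I don't know', and the Appendix I.3 legend provides for a 'None of the above' response.

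**Step 2. The plan's precision, as a yardstick.** Inputs: 280 completed surveys and Equation 1 (Section 9.5). Half-width = 1.96 × √[p(1 − p)/280].
- p = 50%: 1.96 × √(0.25/280) = 5.9 points
- p = 90%: 1.96 × √(0.09/280) = 3.5 points

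All five half-widths in Table 1 (5.9, 5.7, 5.4, 4.7, 3.5) reproduce.

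**Step 3. Illustrative size.** The Protocol gives none of the inputs below; all are assumptions.
- s = share of eligible patients with no other source: 10%, 30%, 50%
- d = fraction of these who stop at Q16: 0 to 100%. The rest tick something untrue.
- Correct understanding differs by 20 points between these patients and the others (60% against 80%, in either direction)

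Formulas:
- Eligible patients reaching Q16 needed for 280 completes = 280/(1 − sd), rounded up
- False Q16 answers among 280 = 280 × s(1 − d)/(1 − sd)
- Shift in the analysed understanding rate = sd(1 − s) × (difference)/(1 − sd)

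Worked case, s = 30% and d = 50%:
- 280/0.85 = 329.4, so 330 patients
- 280 × 0.15/0.85 = 49 false answers
- 0.15 × 0.70 × 20/0.85 = 2.5 points

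| s | d | Patients needed | False Q16 answers of 280 | Shift (points, either sign) |
|---|---|---|---|---|
| 10% | 0 | 280 | 28 | 0 |
| 10% | 25% | 288 | 22 | 0.5 |
| 10% | 50% | 295 | 15 | 0.9 |
| 10% | 100% | 312 | 0 | 2.0 |
| 30% | 0 | 280 | 84 | 0 |
| 30% | 25% | 303 | 68 | 1.1 |
| 30% | 50% | 330 | 49 | 2.5 |
| 30% | 100% | 400 | 0 | 6.0 |
| 50% | 0 | 280 | 140 | 0 |
| 50% | 25% | 320 | 120 | 1.4 |
| 50% | 50% | 374 | 93 | 3.3 |
| 50% | 100% | 560 | 0 | 10.0 |

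The two harms trade off. If nobody stops, Q16 carries the whole error and understanding is untouched. If everyone affected stops, the Q16 answers that remain are true, but patients with no other source have vanished from every result. In both cases 100% of analysed patients report another source, provided at least one tick is enforced.

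**The case against.** **Zero ticks.** Q16 is a multiple-response item, and nowhere does the Protocol say that such an item needs at least one tick. An empty answer could serve as 'none'. The point is fair, so a result of exactly 100% depends on how the survey is programmed. The Protocol's general wording on forced answers points the other way, though, and an empty answer would be uninterpretable without a stated rule.

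**Few will stop.** Q16 is the last content item, and where payment is offered it follows directly. A careless tick is more likely than a break-off. This stands: distortion of Q16 is the main consequence and loss of Q14–Q15 the lesser one.

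**The complete-survey rule is prespecified.** It agrees with a target expressed in completed surveys, and recruitment continues until 280 are reached. Section 9.7 reports both eligible patients and eligible completers, so the total loss is visible. This stands as a defence of the rule as the main analysis. The counts do not show where patients stopped, however, and recruiting more completers does not remove selection.

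**Stronger readings that the documents do not support.** A reader might infer any of the following.
- *That understanding will be inflated.* Those caught by Q16 include patients reached only by the programme's intended route, who may understand as well as others or better.
- *That the doctor-or-nurse route can no longer be assessed.* Q15A and Q15B ask directly whether the doctor or nurse provided the communication and offered to explain it.
- *That a large share of paper respondents will be lost.* An assumed, independent 1–2% blank rate over all 19 responses gives 1 − 0.99^19 = 17% to 1 − 0.98^19 = 32%. That count includes screening items, several of which decide eligibility, and paper is only a contingency. For the six responses in Q14–Q16 the same assumption gives 6% to 11%.
- *That Annex 2 contradicts Section 9.6.* The Annex comment describes the data capture system. Section 9.6 says the same for Internet and telephone, and its missing-data provision covers paper and non-completion.

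**Conclusion.** The point holds for Q16 on the Protocol's text alone. With compulsory answering and no 'None' or 'I don't know', the planned source-of-information result overstates sources other than the doctor or nurse. If a tick is enforced and nobody stops, the overstatement equals the unknown share of patients with no other source: 28, 84 or 140 of 280 at an assumed 10%, 30% or 50%.

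The loss of Q14–Q15 answers for a patient who stops at Q16, or leaves it blank on paper, also follows from Sections 9.6 and 10.2. How often it would happen is not known. The illustrated shifts of 0.5 to 10.0 points rest entirely on assumed shares, break-off fractions and a 20-point difference, and can take either sign. Only the more extreme cases exceed the planned half-widths of 3.5 to 5.9 points. None would overturn a majority conclusion, because both assumed rates, 60% and 80%, lie above one half. No claim about the size or direction of bias in understanding is warranted.

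**What to change.** 1. Add 'None of these' and 'I don't know' to Q16, each exclusive of the other options. This must be done before fielding, because the item cannot be repaired after data collection. Appendix I.3 is still listed as a draft in Annex 1.
2. State in Sections 9.6 and 10.2 that a blank Q16 does not by itself remove an eligible respondent's answers to Q14 and Q15.
3. Report break-offs by question, in addition to the counts of eligible and completing patients already planned.
4. Add a sensitivity analysis of Q14–Q15 that includes every eligible respondent who answered the item. Apart from the exception in item 2, the complete-survey rule can remain the main analysis, and the target of 280 completed surveys need not change.

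The cost is two response options, one sentence on the handling of Q16, and slightly varying denominators in the sensitivity analysis.
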